9.2 ANALYSIS OF ENDPOINTS

9.2.1 Primary Endpoint

For each dosing cohort, the primary endpoint is the proportion of participants who experienced at least one Grade 3 or higher adverse event at or before week 48. It will be analyzed using the safety sample and the PP48 analysis sample. Proportions will be estimated by treatment group together with their 95% confidence intervals derived using the Clopper-Pearson exact method. Although this study is not powered to detect it, a between-group comparison within each dosing cohort will be performed using Fisher's exact test.

9.2.2 Secondary and Exploratory Endpoints

Secondary and exploratory endpoints consist of the following:

1. The proportion of participants who experience at least one Grade 3 or higher adverse event at or before weeks 12, 24 and 36.

Protocol ITN075AI: BRAVOS Brentuximab Vedotin for Systemic Sclerosis

- 2. The proportion of participants who experience at least one Grade 2 or higher adverse event at or before weeks 12, 24, 36, and 48.
- 3. The proportion of participants with Grade 2 or higher peripheral neuropathy at or before weeks 12, 24, 36, and 48.
- 4. The proportion of participants with Grade 3 or higher neutropenia at or before weeks 12, 24, 36, and 48.
- 5. The proportion of participants with any of the following Grade 3 or higher adverse events at or before week 48:
 - a. Peripheral neuropathy.
 - b. Neutropenia.
 - c. Infectious adverse events.
 - d. Infusion reactions, including anaphylaxis and new onset rash consistent with Stevens-Johnson syndrome, toxic epidermal necrolysis, or other drug reaction.
 - e. PML.
- 6. Modified Rodnan Skin Score (mRSS) at weeks 12, 24, and 48.
- 7. Provisional American College of Rheumatology Combined Response Index in Systemic Sclerosis (CRISS) at weeks 24 and 48.
- 8. Percent predicted Forced Vital Capacity (FVC) at weeks 24 and 48 weeks.
- 9. Physician's global assessment on a Likert scale at weeks 24 and 48.
- 10. Patient's global assessment on a Likert scale at weeks 24 and 48.
- 11. Health-related quality of life (HRQOL) assessed by PROMIS-29 version 2.0 at weeks 24 and 48.
- 12. Physical function assessed by the Scleroderma Health Assessment Questionnaire-Disability Index (SHAQ-DI) at weeks 24 and 48.

All secondary and exploratory endpoints at all study weeks will be analyzed using the safety sample. Additionally, endpoints at weeks 12, 24, 36 and 48 will be analyzed using the corresponding PP12, PP24, PP36 and PP48 analysis samples.

The proportions of participants with peripheral neuropathy and the different types of adverse events will be analyzed and compared in the same manner as described above for the primary endpoint. The numbers of AEs and SAEs will be summarized using simple descriptive statistics. Simple descriptive statistics will be provided overall and by treatment group for FVC and the different disease severity scales. In each dosing cohort, the Wilcoxon Signed Rank test will be used to determine if there was a significant change from baseline to the follow-up evaluations within each treatment group. Between-group comparisons within each dosing cohort will be performed using the Wilcoxon Rank Sum test.

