9.2.3 Analysis of Dose-Response Relationship

The 3 dosing cohorts will be merged together to determine if there is a significant dose-response relationship in the endpoints with the amount of brentuximab vedotin received. The 4 dose levels include placebo (0.0 mg/kg), and brentuximab vedotin at low (0.6 mg/kg), medium (1.2 mg/kg), and high dose (1.8 mg/kg). The primary endpoint as well as the proportions of participants with peripheral neuropathy and the different types of adverse events will be analyzed using the exact version of the Cochran-Armitage test for trend. Additionally, these endpoints will be analyzed using a logistic regression model. For FVC and the disease severity scales, the Spearman correlation will be used to determine if there is an association in the change from baseline with the dose level. These analyses will be performed on the safety sample and the PP48 sample.

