9.2.4 Missing Data

Standard procedures will be used to ensure that data are as complete and accurate as possible. Due to the fact that this is primarily a safety study and due to the small sample size in each dosing cohort, no imputation for missing data will be done.

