9.3 SAMPLE SIZE

No formal power analyses were conducted since all safety and efficacy evaluations are exploratory. The total sample size for this study is 24 participants with 8 participants in each of 3 dosing cohorts including 6 participants receiving brentuximab vedotin and 2 receiving placebo. The ability to detect significant events of certain frequencies was considered. Table 2 illustrates the probability of observing at least 1 significant event in a dosing cohort of 6 participants receiving brentuximab vedotin. A cohort of 3 participants has also been included in case there are partially enrolled cohorts.

Table 2 Probability of Events

	True Probability of Event			
	0.1	0.2	0.3	
Probability of observing at least 1 event in 3 participants	0.27	0.49	0.66	
Probability of observing at least 1 event in 6 participants	0.47	0.74	0.88	

Additionally, Table 3 displays the upper and lower limits of the exact 95% Clopper-Pearson confidence interval for the primary outcome among the 6 participants treated with brentuximab vedotin in any dosing cohort.

Table 3 Confidence Limits

Number with Grade 3+ AE	Proportion with Grade 3+ AE	Lower Limit for Exact 95% CI	Upper Limit for Exact 95% CI
0	0.000	0.000	0.459
1	0.167	0.004	0.641
2	0.333	0.043	0.777
3	0.500	0.118	0.882
4	0.667	0.223	0.957
5	0.833	0.359	0.996
6	1.000	0.541	1.000

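### With 6 active and 2 placebo participants per cohort, the planned exact rank-sum test (untied, two-sided 0.05) and the placebo signed-rank test cannot reject, and no pooled drug-versus-placebo test of the efficacy scales is planned

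*Protocol*

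**What the plan says.** Section 9.3 sets the cohort size: "8 participants in each of 3 dosing cohorts including 6 participants receiving brentuximab vedotin and 2 receiving placebo".

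For FVC and the disease severity scales, section 9.2.2 orders two tests per cohort. One is within each treatment group: "In each dosing cohort, the Wilcoxon Signed Rank test will be used to determine if there was a significant change from baseline". The other is between groups: "Between-group comparisons within each dosing cohort will be performed using the Wilcoxon Rank Sum test". The section also promises simple descriptive statistics by treatment group. It does not give the level or sidedness of the tests, or say whether they are exact or asymptotic.

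Section 9.2.3 merges the cohorts, with all placebo participants as dose zero. For these endpoints it plans one analysis: "For FVC and the disease severity scales, the Spearman correlation will be used to determine if there is an association". The binary endpoints get more. They "will be analyzed using the exact version of the Cochran-Armitage test for trend", and the section goes on: "Additionally, these endpoints will be analyzed using a logistic regression model".

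On missing values, section 9.2.4 says that "due to the small sample size in each dosing cohort, no imputation for missing data will be done". A caveat about power appears only for the primary endpoint in section 9.2.1 ("Although this study is not powered to detect it, a between-group comparison within each dosing cohort will be performed using" Fisher's exact test). Section 9.3 calls all evaluations exploratory.

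**The concern.** Low power is normal in a study of this size and the protocol is open about it. A test whose smallest attainable p-value lies above the significance level is a different matter: its result is known before any data arrive.

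Two consequences follow for the efficacy scales.

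- **Asymmetry.** The signed-rank test can reject in six active participants and cannot in two placebo participants. Equal improvement in both groups can therefore be reported as significant change on drug and none on placebo. The protocol presents this trial as the step before a placebo-controlled efficacy study, so that misreading has an audience.
- **No usable drug-versus-placebo contrast.** If the within-cohort comparison cannot reject, only the Spearman correlation remains. It looks for a monotone dose trend. It is also not stratified by cohort, and dose rises with enrolment order over a 260-week enrolment target (section 3.3), so a change in case mix or care between cohorts can look like a dose effect.

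**Working it through.** **The plan's own figures.** Section 9.3 gives no figure for the Wilcoxon tests. Its tables reproduce: 1 − 0.9^6 = 0.469, 1 − 0.8^6 = 0.738 and 1 − 0.7^6 = 0.882 match the six-participant row of Table 2, and the Clopper-Pearson limits match every row of Table 3.

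**Inputs.** 6 active and 2 placebo per cohort, three cohorts (9.3); no imputation (9.2.4). Assumed: exact tests, two-sided 0.05. Power figures assume normal changes with a common SD.

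**Rank-sum test within a cohort.** Without ties, the smallest two-sided exact p-value is 2/C(N, n placebo).

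| Active v placebo | Arrangements | Minimum p |
|---|---|---|
| 6 v 2 (planned) | 28 | 0.071 |
| 5 v 2 (one active value missing) | 21 | 0.095 |
| 8 v 2 | 45 | 0.044 |
| 6 v 3 | 84 | 0.024 |

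Ties can lower the minimum. With active changes 0, 0, 0, 1, 2, 3 and placebo changes 4, 5, the opposite extreme is no longer equally far from the mean, and p = 1/28 = 0.036.

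Power at a 2-SD effect is 0% untied, and 10%, 19% and 23% for whole-number scores with SD 5, 2 and 1 points. At two-sided 0.10 or one-sided 0.05 the untied power would be 57%.

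**Signed-rank test within a group.** The smallest two-sided p-value is 2/2^n:

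- n = 2 (placebo): 2/4 = 0.50 (one-sided 0.25)
- n = 5: 2/32 = 0.0625
- n = 6 (active): 2/64 = 0.031, reached only if all six changes are non-zero and share a sign

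One missing or zero change in an active group thus leaves neither group in that cohort able to reject.

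**Asymmetry.** Suppose both groups improve by 1.5 SD. The chance that all six active changes share a sign is Φ(1.5)^6 + Φ(−1.5)^6 = 0.660. Rounded to whole numbers with SD 5, 2 and 1 points it is 0.60, 0.51 and 0.35. For placebo it is 0.

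**Cohort-stratified alternative.** Add the placebo rank sums over the three cohorts. There are 28^3 = 21,952 equally likely arrangements with mean 27. The test rejects at a sum ≤ 16 or ≥ 38, with exact size 0.041 and minimum p = 2/21,952 = 0.00009.

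**Simulated rejection rates at nominal 0.05** (Spearman cut-off |rho| ≥ 0.415):

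| Scenario | Stratified, all active v placebo | Spearman (planned) | Each dose v pooled placebo, 6 v 6 |
|---|---|---|---|
| 2 SD at every dose | 95% | 73% | 83% |
| 1.5 SD at every dose | 77% | 53% | 58% |
| 2 SD at middle dose only | 12% | 8% | 83% for that dose |
| 2 SD at top dose only | 12% | 73% | 83% for that dose |
| Linear, reaching 2 SD | 60% | 92% | 83% for the top dose |
| No effect, drift 0.5 SD per cohort | 4% | 14% | 9% for first or third dose |
| No effect, drift 1 SD per cohort | 4% | 36% | 19% for first or third dose |

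The drift sizes are assumptions; the protocol gives no basis for them. Repeat simulation agreed to within about 2 points. The usual t-based Spearman cut-off (0.404) raises its power at 2 SD and 1.5 SD by about 3 points.

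**The case against.** **Version and level are not stated.** They may be set in the SAP, which is not at hand. At complete separation an uncorrected normal approximation gives p = 0.0455 (0.067 with continuity correction). This stands as a limit on the rank-sum statement, which is confined to the exact test. It does not rescue the test: the true null probability of that outcome is 0.071, so the nominal rejection is an artefact. The placebo signed-rank test fails either way, since its normal approximation gives 0.16 to 0.18.

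**Ties are common.** mRSS and the Likert scales produce them, and the test can then reject. That is right, and the 10% to 23% powers above show how far it helps.

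**The plan already covers part of this.** Descriptive statistics are promised, all evaluations are labelled exploratory, and nowhere is a significant active group alone said to show a drug effect. All true. That is why the point is minor, but it does not supply a test that can reject or prevent the misreading.

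**Spearman is often the better test.** This stands wherever the effect rises with dose: 92% v 60% for the linear effect and 73% v 12% for top dose only. At smaller effects neither test is strong: for 1 SD at every dose the stratified test has about 43% power and Spearman about 30%; for 0.5 SD, about 14% and 11%. Spearman should stay, and the stratified test answers a different question.

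**More p-values.** Section 9.2.2 lists 15 efficacy endpoint-visits (mRSS at three, six others at two each). Four added tests in two analysis samples would give up to 15 × 4 × 2 = 120 more. This is a fair cost and argues for labelling the additions exploratory.

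**Conclusion.** The concern holds and is minor. At the planned 6 v 2, the exact rank-sum test without ties cannot reach two-sided 0.05 (minimum 0.071). The signed-rank test in two placebo participants cannot reject at any usual level (minimum 0.50 two-sided, 0.25 one-sided).

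The rank-sum part depends on the assumed level, the exact version, the absence of ties and the planned cohort size. Replacements under section 4.5, or participants added under section 8.11.2, could enlarge a cohort enough to lift it (8 v 2 or 6 v 3). The placebo signed-rank part is firmer: two-sided 0.05 would need at least six placebo participants in a cohort.

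Nothing here touches the primary endpoint, the binary safety analyses or dose escalation, which rests on Safety Review Committee review. What is at stake is how exploratory efficacy results are read.

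**What to change.** In section 9.2.2:

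- Report within-cohort placebo results for FVC and the severity scales descriptively, and drop the signed-rank test in the two-person placebo groups.
- State that a significant within-group change in an active group alone is not read as a drug effect.

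For the same endpoints, beside the trend tests of section 9.2.3:

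- Add an exact all-active versus placebo rank-sum test stratified by cohort. It uses only comparisons within the randomised cohorts.
- Add each dose versus placebo pooled across cohorts (6 v 6) as a supportive comparison, with placebo also shown by cohort.

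Keep the Spearman correlation, and leave section 9.2.1 and the binary analyses as they are.

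The cost is wording; no new data are needed. Three drawbacks should be stated with it. In each 6 v 6 comparison, 4 of the 6 controls were not randomised alongside that dose, so drift can inflate false positives. The stratified test is weaker than Spearman when the effect is linear or confined to the top dose, and like Spearman it is weak when only the middle dose works. The added tests are exploratory and unadjusted for multiplicity.

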9.2.3 Analysis of Dose-Response Relationship

The 3 dosing cohorts will be merged together to determine if there is a significant dose-response relationship in the endpoints with the amount of brentuximab vedotin received. The 4 dose levels include placebo (0.0 mg/kg), and brentuximab vedotin at low (0.6 mg/kg), medium (1.2 mg/kg), and high dose (1.8 mg/kg). The primary endpoint as well as the proportions of participants with peripheral neuropathy and the different types of adverse events will be analyzed using the exact version of the Cochran-Armitage test for trend. Additionally, these endpoints will be analyzed using a logistic regression model. For FVC and the disease severity scales, the Spearman correlation will be used to determine if there is an association in the change from baseline with the dose level. These analyses will be performed on the safety sample and the PP48 sample.

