6.2 RANDOMIZATION, BLINDING, AND UNBLINDING

6.2.1 Randomization

Participants who meet the eligibility criteria will be randomly assigned to a study treatment group, either brentuximab vedotin or placebo control. Enrollment is defined as the time of random assignment. Participants will be randomly assigned to their treatment group utilizing a centralized, automated randomization system. Randomization will not be stratified.

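### The pooled dose-response test for FVC and the disease severity scales leaves out the baseline value: valid overall, but less precise than it could be and distorted when the dose groups differ at baseline

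*Protocol*

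**What the plan says.** Section 9.2.3 of the protocol sets the pooled analysis: "The 3 dosing cohorts will be merged together to determine if there is a significant dose-response relationship in the endpoints". The levels are placebo and 0.6, 1.2 and 1.8 mg/kg. Binary endpoints get an exact trend test and also a logistic regression. The remaining measures, namely FVC and the severity scales, get one method only: "the Spearman correlation will be used to determine if there is an association in the change from baseline with the dose level". No covariate is mentioned.

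Section 9.3 plans "8 participants in each of 3 dosing cohorts including 6 participants receiving brentuximab vedotin and 2 receiving placebo", which gives 6 participants at each of the four levels once placebo is pooled. Section 6.2.1 adds that "Randomization will not be stratified". Under section 3.1 each higher dose opens only after the safety committee has reviewed the previous cohort. Randomization is therefore between drug and placebo within a cohort, not between doses. Section 9.3 also says: "No formal power analyses were conducted since all safety and efficacy evaluations are exploratory".

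Appendix 1 already schedules pre-treatment values: mRSS at screening and week 0, spirometry at screening, and the global assessments, PROMIS-29 and SHAQ-DI at week 0.

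**The concern.** A change score contains its own baseline with a negative sign. Unless follow-up tracks baseline perfectly, participants who start high tend to fall and those who start low tend to rise, whatever their treatment. If one dose level happens to start higher than another, part of that difference passes into the correlation of change with dose. Entry mRSS may lie anywhere from 15 to 45 (section 4.1), groups are of 6, and nothing in the design balances baseline across doses.

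At stake is the only inferential efficacy analysis that uses all cohorts together. With 24 participants there is little precision to give away, and the information that would recover some of it is already in the database.

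**Working it through.** **The plan's own figures.** The protocol gives no figure for this analysis. Its only design figures, Tables 2 and 3 in section 9.3, concern event rates. They reproduce as printed (for example 1 − 0.9^6 = 0.47) and are not affected.

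**Inputs from the protocol.** Four levels, 6 participants each, N = 24; outcome is change from baseline; no covariate.

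**Assumptions not in the protocol.** Baseline-to-follow-up correlation r from 0.3 to 0.9; equal SDs at both times; normal data; linear dose effect; two-sided 0.05. The placebo-to-top-dose difference is 8/8.7 = 0.92 SD. This corresponds to 8 mRSS units if entry scores were spread uniformly over 15 to 45, since 30/√12 = 8.7.

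**Precision.** The variance of a change score is 2(1 − r)σ². After adjustment for baseline it is (1 − r²)σ². The ratio of adjusted to unadjusted is (1 + r)/2. Estimating the baseline slope with N = 24 costs a factor of about 21/20.

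| r | (1+r)/2 | × 21/20 |
|---|---|---|
| 0.3 | 0.65 | 0.68 |
| 0.5 | 0.75 | 0.79 |
| 0.7 | 0.85 | 0.89 |
| 0.8 | 0.90 | 0.95 |
| 0.9 | 0.95 | 1.00 |

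The gain is clear at low r and gone at about r = 0.9.

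**How large imbalance can be by chance.** The difference between two baseline means of 6 has SD √(2/6) = 0.58 baseline SD. It exceeds 0.5 SD with probability 39% and 1 SD with probability 8%. The four level means span at least 1 SD in 31% of simulated trials. A 0.5 SD imbalance shifts the unadjusted contrast by (1 − r) × 0.5 SD: 0.35 SD at r = 0.3, 0.15 SD at r = 0.7 and 0.05 SD at r = 0.9.

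**Simulation.** Spearman correlation of change with dose (22 df) against partial Spearman given baseline (21 df). The worst imbalance is the 20% of null trials with the largest baseline-dose correlation in absolute value.

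| r | Power, unadjusted → adjusted | Type I error in worst-imbalance fifth, unadjusted |
|---|---|---|
| 0.3 | 26% → 34% | 12–14% |
| 0.5 | 34% → 41% | 11% |
| 0.7 | 52% → 56% | 8% |
| 0.8 | 69% → 71% | 7% |
| 0.9 | 93% → 93% | 6% |

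In that same fifth the adjusted test stays at about 5 to 6%. Over all null trials both tests are at about 5%. Coarse, tied scores give the same pattern.

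**Share of the noise.** Under the null, baseline-dose imbalance accounts for 32%, 22%, 13%, 8% and 4% of the variance of the unadjusted coefficient as r goes from 0.3 to 0.9.

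**The case against.** The strongest reply is that nothing stated is wrong. A Spearman test on change scores holds its error rate, and chance imbalance is already counted in that 5%. Efficacy is exploratory and no power is claimed. The size of the gain depends on r, SD and effect, none of which the protocol gives, and it is nil at high r. The protocol does not bar a supplementary adjusted analysis in the SAP. With no imputation (section 9.2.4) and a repeat in PP48, N may fall below 24 and shrink the gain. All of this stands and keeps the point small. It does not remove the point, because the protocol itself fixes the unadjusted statistic and the better one needs no new data.

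Four stronger readings are tempting and are not supported.

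- A reader might infer that baseline imbalance determines the result, or biases it. Imbalance explains 4 to 32% of the null variance, and the shift from chance imbalance averages zero over trials. It distorts individual unlucky trials.
- A reader might infer that this test selects the dose for a later trial. Sections 1.1 and 1.4.2 foresee a later efficacy study but give this analysis no such role.
- A reader might extend the point to section 9.2.2, where "Between-group comparisons within each dosing cohort will be performed using the Wilcoxon Rank Sum test". With 6 against 2, the smallest two-sided exact p-value is 2/28 = 0.071. That test cannot reach 0.05 with or without baseline, so adjustment is not its problem.
- A reader might take all imbalance between doses to be chance. Cohorts enrol one after another within a 260-week enrollment target (section 3.3), so case mix may also drift. Adjustment reduces this but does not remove it.

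**Conclusion.** The point holds as a minor matter of efficiency and robustness. The planned correlation is valid overall but gives up precision, and it is vulnerable when the dose groups start from different levels. Under the assumptions above, the power lost runs from about 8 points at r = 0.3 to none at r = 0.9. Type I error in the worst-imbalance fifth of trials runs from about 12–14% down to about 6%. The power figures are scaled to mRSS; for FVC and the other scales they apply only as far as the same r and standardized effect do. The primary safety analysis and every printed design figure are untouched.

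**What to change.** In section 9.2.3, add one sentence. For each scale with a baseline measurement, a partial Spearman correlation (rank ANCOVA) of change with dose level, given the participant's baseline value, will be computed in the same samples. CRISS is excluded because it is a composite response index. Keep the planned unadjusted coefficient, report the two side by side, and label both exploratory. Add a note that adjustment does not remove case-mix drift between sequential cohorts.

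The cost is that sentence and one degree of freedom (22 to 21 with all 24 participants). No new data, visits or participants are needed.
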